Enrollment of the planned 24 pts is completed and all received at least one dose of MK-3475 (pembrolizumab). Median age is 67 (44-85); 18 are male. All but 1 patient (stage IB) had advanced disease (stages IIB-IV); 2 IIB, 3 IIIA, 3 IIIB, 15 with IVA. 15 of 24 were SS. Most pts were heavily treated with median of 4 prior systemic therapies (range 1-10). Nine pts have confirmed clinical response (38% ORR; 8 PR, 1 CR) and 5 of these responders are continuing on therapy with median follow-up of 49 weeks. Of the 9 current responders, 5 are Mycosis Fungoides (2 IIB, 2 IIIA, 1 IIIB; 4, 6, 3 and 7 prior systemic therapies) and 4 SS (4 IVA; 1, 3, 4, and 6 prior systemic therapies). Two of the PRs are in near global CR; both are SS with complete clearing of circulating Sézary cells. Four pts had deep skin response with >90% mSWAT reduction (3 SS, all IVA; 1 Mycosis Fungoides, IIIA). Median time to response is 11 weeks (range 8-22 weeks). Median PFS is 44 weeks and 75% were progression-free at 6 months by KM estimate. To

[figure not shown]
date, related AEs reported in greater than 5% of patients are dermatitis (n=6), anemia (n=3), leukopenia (n=3), elevated liver enzymes (n=2), diarrhea (n=2), and pneumonitis (n=2). Most AEs were grade 1-2 and limited to AEs previously reported with MK-3475 (pembrolizumab) in other malignancies. Grade 3/4 AEs were immune mediated exfoliative dermatitis (n=2), anemia (n=2), elevated liver enzymes (n=1), pneumonitis (n=1), and hyperuricemia (n=1). Only two MK-3475 (pembrolizumab) related SAE's were reported including one grade 3 pneumonitis and one grade 3 diarrhea secondary to steroid refractory duodenitis. In one patient with moderate immune-mediated skin disease flare, we observed significant tumor-infiltrating CD8+ T cells, followed by clinical response.

Planned and ongoing correlative studies include those to characterize the tumor microenvironment (IHC/multiparametric, nanostring gene expression profiling, multiplexed ion beam imaging), systemic immune response (flow cytometry, CyTOF, Luminex cytokine profiling), and the molecular/genomic immune profile (exome sequencing, neoantigen discovery, high throughput sequencing of TCR).

[figure not shown]

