#### 13.1.1.4 *Interim Safety and Futility Analyses*

- One interim safety analysis will be performed in this study when 12 patients are evaluable for toxicity at pre-C4 (week 10) of the study. If at that time, 4 or more patients have experienced study drug related serious adverse events (SAEs), we will conclude that the combination immunotherapy regimen is too toxic and accrual will stop.
- The properties of interim safety stopping rule are given in the table below.

True Probability of Study Drug Related SAEs (ptox)	Probability of Stopping Early (pstope)
0.10	0.026
0.14	0.075
0.18	0.155
0.22	0.261
0.26	0.382
0.30	0.507

One interim futility analysis will be performed in this study. Results will be reviewed by the participating institutions/investigators, CITN, NCI/CTEP, and participating industry sponsors (Horizon and Merck).

The statistical criterion for success requires ORR that is greater than 37% (null) and at least 65% (alternative). This is a single stage trial. Patients will be recruited continuously. We will perform the interim futility analysis when 12 patients have been followed for 6 months. If ORR is less than 33% (4 or less CR+PR), the trial will stop and we will accept the null that combination therapy is no better than monotherapy. The probability of

stopping at interim futility analysis under the null and alternative are 52% and 2% respectively.

Otherwise, the trial will continue until we reach 30 patients. If ORR is at least 57% (17 or more CR+PR) at the final analysis, we will accept the alternative that combination therapy is significantly better than monotherapy. The type I error rate is 2%. The power is 87%.

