#### 13.1.3 Sample Size/Accrual Rate

##### 13.1.3.1 *Power and Sample Size*

The statistical criterion for success requires ORR that is greater than 37% (null) and at least 65% (alternative). By adding an interim futility analysis, the sample size is 30

patients. The probability of stopping at interim futility analysis under the null and alternative are 52% and 2%, respectively. The type I error rate is 2%. The power is 87%. The expected sample sizes under the null and alternative are 21 and 30, respectively.

This is a single stage trial. Patients will be recruited continuously. We will perform the interim futility analysis when 12 patients have been followed for 6 months. If ORR is less than 33% (4 or less CR+PR), the trial will stop and we will accept the null that combination therapy is no better than monotherapy. Otherwise, the trial will continue until we reach 30 patients. If ORR is at least 57% (17 or more CR+PR) at the final analysis, we will accept the alternative that combination therapy is significantly better than monotherapy.

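### Group 1: reaching 17/30 supports an ORR above the fixed 37%, not a conclusion that the combination is significantly better than monotherapy

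*Combined protocol and SAP*

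**What the plan says.** The Schema lists no control for the trial, and Section 5.2.1 describes Group 1 as single-arm and open-label. The efficacy table in Section 13.1 gives the primary method as a binomial proportion.

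Section 13.1.1.4 sets the hypotheses: "The statistical criterion for success requires ORR that is greater than 37% (null) and at least 65% (alternative". It then gives the rule:

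- Interim, 12 patients followed for 6 months: "If ORR is less than 33% (4 or less CR+PR), the trial will stop".
- Otherwise, "the trial will continue until we reach 30 patients".
- Final: "If ORR is at least 57% (17 or more CR+PR) at the final analysis", then "we will accept the alternative that combination therapy is significantly better than monotherapy".

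The same conclusion is attached to the same count in Sections 1.1.1, 5.2.1, 13.1.1.1 and 13.1.3.1. Section 13.1.3.1 gives the operating characteristics, in percent: "The type I error rate is 2%. The power is 87".

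The only pembrolizumab monotherapy response data for this disease are in Section 2.4.3, on the 24-patient CITN-10 trial: "Nine pts have confirmed clinical response (38% ORR; 8 PR, 1 CR". Sections 2.4.5 and 2.5 put the pembrolizumab monotherapy rate at about 33%. No section says where 37% comes from, gives an interval for the historical rate, or plans a sensitivity analysis on it.

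**The concern.** The hypothesis tested and the conclusion drawn are different statements. The test compares one observed proportion with a constant. The conclusion compares two treatments, and the rate for one of them is known only from 24 patients in another trial. The 2% error rate belongs to the first statement, but a reader will attach it to the second.

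This matters because the sentence is the decision rule for the primary objective, repeated in five places, and not loose background wording. Followed as written, a result exactly at the cut-off would be reported as a significant comparative finding with a 2% chance of error, although the trial contains no comparison that supports it.

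**Working it through.** **Inputs.** Null 0.37, alternative 0.65, stop at 4 or fewer of 12, succeed at 17 or more of 30 (Section 13.1.1.4). CITN-10: 9 responders (8 PR, 1 CR) of 24 (Section 2.4.3). Monotherapy rate of about 33% (Sections 2.4.5 and 2.5).

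**1. The plan's own figures.** With X1 responders among the first 12 patients and X2 among the next 18,

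P(success | p) = sum over x = 5 to 12 of P(X1 = x; 12, p) × P(X2 ≥ 17 − x; 18, p).

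| Quantity | Stated | Recomputed |
|---|---|---|
| Type I error, p = 0.37 | 2% | 0.0215 |
| Power, p = 0.65 | 87% | 0.866 |
| Stop at interim, p = 0.37 | 52% | 0.525 |
| Stop at interim, p = 0.65 | 2% | 0.0255 |
| Expected n, null / alternative | 21 / 30 | 20.6 / 29.5 |

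The design figures reproduce, apart from a trivial rounding difference in the second stopping probability. The arithmetic is not at fault.

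**2. How well the monotherapy rate is known.** 9/24 = 37.5%. The exact (Clopper-Pearson) 95% CI is 18.8% to 59.4%.

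**3. The cut-off result set against CITN-10.** 17/30 − 9/24 = 56.7% − 37.5% = 19.2 points. For a 95% CI by Newcombe's method, the Wilson limits are 39.2% to 72.6% for 17/30 and 21.2% to 57.3% for 9/24:

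- Lower: 0.192 − √[(0.567 − 0.392)² + (0.573 − 0.375)²] = 0.192 − 0.264 = −0.072
- Upper: 0.192 + √[(0.726 − 0.567)² + (0.375 − 0.212)²] = 0.192 + 0.228 = 0.420

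Tests on 17/13 against 9/15:

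| Test | Two-sided p | One-sided p |
|---|---|---|
| Fisher | 0.183 | 0.130 |
| Chi-square, uncorrected | 0.161 | – |
| Boschloo | 0.177 | 0.088 |

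None is below 0.05, so the answer does not depend on the choice of test or its sidedness.

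**4. Error rate of the rule by true monotherapy rate.** If the combination adds nothing, its ORR equals the monotherapy rate p, and the formula in step 1 gives the chance of declaring success:

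| True monotherapy ORR | P(declare success) |
|---|---|
| 30% | 0.2% |
| 33% | 0.6% |
| 37% | 2.15% |
| 37.5% | 2.5% |
| 38% | 2.8% |
| 40% | 4.7% |
| 45% | 13% |
| 50% | 29% |

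Every row lies inside the CITN-10 interval. The 2% is the error rate at 37%: it is smaller below that value and larger above it.

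**The case against.** Testing against a fixed reference rate is ordinary in single-arm phase II work. The protocol is open about having no control, and it states the 37% null in the same subsection as the conclusion, so a careful reader can see what is tested. The Fisher comparison is not part of the plan. Section 13.1.5.2 already asks for 95% confidence intervals, and at 17/30 the exact interval is 37.4% to 74.5%, which excludes 37%. All of this stands. It defends the design and the cut-off, but not the sentence attached to them. That same interval still contains CITN-10's own 37.5%.

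Three stronger readings are tempting, and the documents do not support them.

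- **That 37% is the CITN-10 rate.** 9/24 is 37.5%, so the inference is natural. But no section says so: the documents round 9/24 to 38% and elsewhere use about 33%. The most that can be said is that the source is missing.
- **That the real error rate is several times 2%.** This holds at the higher rates only. At the documents' own 33% it is 0.6%, and at 38% it is 2.8%. Averaging over a Jeffreys posterior from 9/24 gives about 10%, but that prior is an assumption made for this check, the average is not a type I error rate, and about 47% of that posterior lies below 37%.
- **That a claim of superiority should wait until the interval for the difference from CITN-10 excludes zero.** That needs 20/30 by Newcombe's interval (lower limit +2.5 points, where two-sided Fisher is still 0.054) or 21/30 by two-sided Fisher (p = 0.027). At a true 65%, the chance of reaching those counts is 51% or 36%, against 87% for 17/30. The comparison would also be unadjusted and across trials: CITN-10 dosed by weight and all but one of its patients had stage IIB-IV disease, while Group 1 uses a flat dose and admits stages IB-IVB. Using it as a gate would replace one over-reading with another.

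**Conclusion.** The concern holds as a mismatch between test and conclusion. Meeting 17/30 supports an ORR above 37%; it does not establish that the combination is significantly better than monotherapy. At the cut-off, the only monotherapy data in the protocol leave a difference of 19 points with a 95% CI from -7 to +42. The 2% error rate is right at a true monotherapy rate of 37%, and over 33% to 50% it runs from 0.6% to 29%.

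These figures assume that CITN-10 is the relevant reference and that the two trials' patients and response assessments are comparable; the documents establish neither. A reader might infer from p = 0.18 that the cut-off is too low or that the combination would have failed. Neither follows. The comparison shows only that 24 reference patients are too few to carry the comparative claim. The sample size, the cut-off and the stated 2% and 87% are not in question.

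**What to change.** 1. In Sections 1.1.1, 5.2.1, 13.1.1.1, 13.1.1.4 and 13.1.3.1, replace the conclusion at 17 or more responders with: *conclude that ORR exceeds the 37% reference rate*.
2. State where 37% comes from and how it relates to the 38% in Section 2.4.3 and the roughly 33% in Sections 2.4.5 and 2.5.
3. State that 2% is the type I error rate at a true rate of exactly 37%, and add a short sensitivity table of the error rate for reference rates on both sides of 37%, such as the one in step 4 of the working.
4. Report the difference in ORR from CITN-10 with its 95% CI, labelled descriptive and not used as a condition for any conclusion.

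The cost is wording and one table. The 17/30 cut-off, n = 30 and the 87% power are unchanged. The downside is a more modest headline claim.

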#### Summary of Interim Safety and Futility Analyses Strategy

Key Endpoints for Interim Analysis	Timing of Interim Analysis	Purpose of Interim Analysis
Study drug related serious adverse events (SAEs)	12 subjects enrolled and received at least 1 dose of either IFN-g or MK-3475 (pembrolizumab), with 12th pt evaluable through interim safety assessment time point at pre-C4/week 10	Stop for significant safety concerns. Enrollment will not stop in order to wait for the 12th patient to reach week 10. New patient enrollment will continue as long as there are less than 4 study drug-related SAEs.
Overall response rate (ORR) per global assessment of Mycosis Fungoides and Sézary Syndrome (confirmed & investigator assessed)	12 subjects enrolled and received at least 1 dose of either IFN-g or MK-3475 (pembrolizumab); all 12 subjects followed for 6 months	Stop for futility of combination therapy relative to monotherapy.

#### 13.1.2 Exploratory Correlative Analyses

Clinical response (as measured by the primary and secondary endpoints) to combination immunotherapy regimen as a function of biomarkers will be evaluated. All biomarker assays will be run on the clinical trial samples in a blinded manner.

Time to event endpoints (DOR, PFS, EFS) will be evaluated using Kaplan-Meier curves generated by biomarker scoring group using the log-rank test.

Exploratory outcomes will be summarized with descriptive statistics (primarily proportions and medians) for all biomarkers described above, and additionally, serum IL-10, regulatory T-cells, and activated CD8 T cells. Scatterplots and Kendall's tau estimates will be produced for estimating correlation of PD-1, PDL1, or PD-L2 expression measures and clinical outcome across compartments (skin, lymph node, blood). Comparison of tissue IHC markers between pre-treatment and with clinical response or disease progression will be assessed using Wilcoxon signed-rank test. A full panel of approximately ~600 mRNA transcripts will be measured using the Nanostring platform and will be evaluated using descriptive statistics.

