## 2.5 Correlative Studies Background (Treatment Group 1)

The proposed trial provides a rich context for the investigation of biomarkers for anti-PD1 therapy. Treatment of cutaneous T cell lymphomas with MK-3475 (pembrolizumab) monotherapy produced a response rate of ~33%, and we expect that the addition of interferon gamma will result in an even higher rate of clinical response. This high rate of response will improve our statistical power in discovering novel biomarkers. Additionally, as a cutaneous malignancy with frequent leukemia, CTCL affords the opportunity for serial collection of high quality biopsies of skin and blood. Thus, from an exploratory biomarker perspective, this disease offers an opportunity to investigate the determinants of response and resistance to anti-PD-1 and immune therapies, as well as to discover additional molecular targets governing immune dysregulation in cancer.

Correlates will focus on potential predictive biomarkers for PD-1 therapy (e.g., as expression of PD-L1 and mutational/neoantigen burden) and assessment of the effects of IFN-gamma (e.g., Th1 vs Th2 skewing). The addition of interferon gamma is hypothesized to affect the tumor microenvironment in two ways: 1) IFN-gamma will upregulate PD-L1 expression on suppressive cell populations. 2) IFN-gamma will skew CD4 T cells towards a Th1 phenotype. Sampling time points have been selected to explore these effects.

The majority of proposed biomarkers are designed to be hypothesis-generating by applying novel technologies such as multiple ion beam imaging and CyTOF to provide means to analyze the effects of checkpoint blockade both systemically and in the tumor microenvironment in an unprecedented manner. We anticipate that these studies will yield candidate biomarkers that correlate with prognosis, have predictive value in the selection of which subjects benefit from anti-PD1/IFN-gamma immunotherapy, and will investigate the hypothesis that Th1 skewing of the T cell repertoire can potentiate immune checkpoint blockade therapy.

Assays may include but are not be limited to:

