**Summary Analysis Strategy for Efficacy Endpoints**

Endpoint/Variable (Description, Time Point)	Statistical Method	Analysis Population	Missing Data Approach
Primary:			
Overall response rate (ORR) per global assessment of Mycosis Fungoides and Sézary Syndrome (confirmed & investigator assessed)	Binomial proportion	Evaluable population as defined	Subjects without any efficacy evaluation will be excluded; if one compartment is missing data, that compartment will be considered non-response
Secondary:			
Time to Response (TTR)	Simple statistics	All responders	Non-responders are excluded in analysis
Duration of Response (DOR)	Kaplan-Meier method	All responders	Non-responders are excluded in analysis; censored at last f/u or start of new significant therapy
Progression-free survival	Kaplan-Meier method	All efficacy or safety evaluable patients	Censored at last f/u or start of new significant therapy

Endpoint/Variable (Description, Time Point)	Statistical Method	Analysis Population	Missing Data Approach
Event-free survival	Kaplan-Meier method	All efficacy or safety evaluable patients	Event is defined by early termination due to toxicity, start of new significant therapy, PD, or death of any cause
Rate of overall response duration beyond 12 months (ORR12) per global assessment of Mycosis Fungoides and Sézary Syndrome (confirmed & investigator assessed)	Binomial distribution	Evaluable DOR beyond 12 months for evaluable population.	Subjects without any efficacy evaluation will be excluded; The ORR12 is the proportion of ORR times conditional probability of DOR beyond 12 months. If one compartment is missing data, that compartment will be considered non-response. Censored at last f/u. Start of new significant therapy before 12 months will be considered as failures.

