Biomarker Name a AND Lead PI and Site	Assay (CLIA: Y/N)	Use (Integral, Integrated, or Exploratory) AND Purpose b	Tissue/Body Fluid Tested and Timing of Assay	M/O	Funding Source(s) c
Gene expression profiling  PI: [name]  Site: Fred Hutchinson Cancer Research Center	Nanostring immune panel  CLIA: N	Exploratory  Purpose: Hypothesis generating and will assess Th1 skewing of T cells after interferon gamma treatment	Tissue: Skin biopsy and peripheral blood mononuclear cells  Timing:  (M) Skin biopsy: Prior to IFN-gamma lead-in, Prior to Cycle 1, Prior to Cycle 2, at progression or appearance of a new lesion, at end of treatment and in the event of a Skin Flare Reaction  Blood draw: Prior to IFN-gamma lead-in, Prior to Cycle 1, Prior to Cycle 2, Prior to Cycle 6, with a response, at progression or appearance of a new lesion, at end of treatment and in the event of a Skin Flare Reaction  (O) Skin biopsy: At response (PR/CR),	M	(see above)
Peripheral blood immunophenotyping  PI: [name]  Site: Stanford University	Multiparametric flow cytometry and CyTOF  CLIA: N	Exploratory  Purpose: Hypothesis generating  Phenotyping of normal T cell and Sezary cell populations pretreatment and post treatment. Functional phenotyping of T cells will be performed by testing cytokine production after stimulation.	Tissue: Peripheral blood mononuclear cells  Timing:  (M) Prior to IFN-gamma lead-in, Prior to Cycle 1, Prior to Cycle 2, and in the event of a Skin Flare Reaction.	M	(see above)
Serum cytokine and chemokine detection  PI: [name]  Site: Stanford University	Luminex multiplexed ELISA-based cytokine assay  CLIA: N	Exploratory  Purpose: Hypothesis generating  Quantitative measurement of cytokines/chemokines pre and post treatment	Tissue: Serum  Timing:  (M) Prior to IFN-gamma lead-in, Prior to Cycle 1, Prior to Cycle 2, prior to Cycle 6, with response, or progression, at EOT and in the event of a Skin Flare Reaction.	M	(see above)

NCI Protocol #: CITN-13  
 Version Date: March 03, 2020

Biomarker Name a AND Lead PI and Site	Assay (CLIA: Y/N)	Use (Integral, Integrated, or Exploratory) AND Purpose b	Tissue/Body Fluid Tested and Timing of Assay	M/O	Funding Source(s) c

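### Group 1: the only planned test of biomarkers against DOR, PFS and EFS is a log-rank test between undefined scoring groups; for quantitative markers a Cox model on the full scale would usually have more power

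*Combined protocol and SAP*

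**What the plan says.** Objective 1.3.1 sets out to relate a list of putative biomarkers to safety, ORR, DOR, PFS and EFS in Treatment Group 1. For the time-to-event outcomes, section 13.1.2 gives one method: "Time to event endpoints (DOR, PFS, EFS) will be evaluated using Kaplan-Meier curves generated by biomarker scoring group using the log-rank test". Neither that section nor any other says what a scoring group is, how many there are, which markers are scored, or where the cuts fall. No Cox or other time-to-event regression is named.

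Many of the markers are quantitative. Appendix C describes the cytokine assay as "Quantitative measurement of cytokines/chemokines pre and post treatment". Sections 2.5.5, 2.5.6, 2.5.8 and 2.5.9 describe mutational and neoantigen burden, CyTOF and flow populations, TCR repertoire diversity, and the Kyn/Trp ratio.

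Section 13.1.2 does use the full scale in one place: "Scatterplots and Kendall's tau estimates will be produced for estimating correlation of PD-1, PDL1, or PD-L2 expression measures and clinical outcome". That covers three expression markers only, and no handling of censoring is stated. The same section assigns descriptive statistics to the Nanostring panel.

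On numbers, section 13.1.3.1 says: "Otherwise, the trial will continue until we reach 30 patients". The efficacy table in 13.1.1 restricts DOR to responders: "Non-responders are excluded in analysis; censored at last f/u or start of new significant therapy". Section 2.4.5 states that the correlatives are exploratory and are not endpoints.

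**The concern.** A log-rank test needs groups. Cytokine levels, Kyn/Trp ratios, TCR diversity, neoantigen burden and CyTOF fractions have no categories defined in the documents, so someone must choose a cut before the planned test can be run.

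The cut has two consequences. Patients on the same side of it are treated as alike, which discards information and, under a smooth dose-response, lowers power. And because the cut is not fixed, the result depends on a choice that can still be made after outcomes are known. With 30 patients at most, and only responders for DOR, there is little information to spare. At stake is whether the trial detects marker associations that its own data could show, and how readily a reader can interpret those it reports.

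**Working it through.** **The plan's own figures.** No alpha, power, effect size or event count is stated for the biomarker tests. The only Group 1 error rates for efficacy belong to the ORR design (stop at 4 or fewer of 12; success at 17 or more of 30; 37% against 65%). Exact binomial calculation gives type I error 2.15% and power 86.6%, agreeing with the stated 2% and 87%. Nothing there speaks to the biomarker tests, so what follows rests on stated assumptions.

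**Inputs from the documents**
- 30 patients (13.1.3.1).
- Median PFS of 44 weeks on pembrolizumab monotherapy (2.4.3), used only to gauge event numbers. With exponential survival, events by 1 year = 30 × (1 − 2^(−52/44)) ≈ 17, and by 2 years = 30 × (1 − 2^(−104/44)) ≈ 24.
- DOR in responders only: 17 at the success boundary, 0.65 × 30 = 19.5 at the alternative. I use 18.

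**Assumptions**
- Normally distributed marker, log-linear effect, hazard ratio (HR) per SD of 1.5, 1.75 or 2.0, two-sided 5%.
- Grouping by median split, with a three-group trend test as an alternative.

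**Approximation.** With D events and β = ln(HR per SD), power is about Φ(√D·β − 1.96) on the continuous scale and Φ(√(D·2/π)·β − 1.96) after a median split. At D = 20:

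| HR per SD | Continuous | Median split | Loss (points) |
|---|---|---|---|
| 1.5 | Φ(1.81 − 1.96) = 44% | Φ(1.45 − 1.96) = 30% | 14 |
| 1.75 | Φ(2.50 − 1.96) = 71% | Φ(2.00 − 1.96) = 51% | 19 |
| 2.0 | Φ(3.10 − 1.96) = 87% | Φ(2.47 − 1.96) = 70% | 18 |

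Losses are taken before rounding.

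**Simulation, 30 patients, about 20 events** (2,000 trials per setting; Cox Wald test against log-rank):

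| HR per SD | Cox, continuous | Median split | Loss | Three-group trend | Loss |
|---|---|---|---|---|---|
| 1.5 | 40.5% | 28.3% | 12 | 33.2% | 7 |
| 1.75 | 66.7% | 46.1% | 21 | 55.1% | 12 |
| 2.0 | 80.2% | 60.5% | 20 | 69.8% | 10 |

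With no effect, these tests reject in 5 to 6% of trials, so the gap is not bought with extra false positives.

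**Simulation, 30 patients, about 23 events** (44-week median, censoring uniform on 52 to 156 weeks, 4,000 trials): the continuous marker gives 44%, 69% and 84%, a median split 32%, 48% and 63%. The losses are 12, 21 and 21 points. A top-quartile cut does little better than the median (33%, 52%, 65%).

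**DOR, 18 responders:**

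| HR per SD | About 12 events: Cox / split / loss | About 9 events: Cox / split / loss |
|---|---|---|
| 1.5 | 24.0% / 18.2% / 6 | 19.4% / 16.0% / 3 |
| 1.75 | 39.7% / 28.1% / 12 | 31.8% / 22.7% / 9 |
| 2.0 | 55.8% / 38.7% / 17 | 43.8% / 31.3% / 12 |

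The DOR losses are smaller partly because neither test has much power with so few events.

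**Threshold instead of log-linear effect** (30 patients, 44-week median, same censoring). If risk steps up at the median and the cut is placed there, the log-rank gives 29%, 45%, 58% and 75% at HR 2, 2.5, 3 and 4, against 25%, 39%, 53% and 68% for the continuous test: grouping leads by 4 to 7 points. If the step is at the top quartile and the cut is placed exactly there, the figures are 26%, 41%, 51% and 65% against 16%, 26%, 34% and 46%: grouping leads by 10 to 19 points.

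**The case against.** The strongest reply is that the direction of the gain depends on the unknown shape of the dose-response. Where the effect is a true threshold and the cut sits on it, grouping wins: modestly at the median, by more at the top quartile. That stands, and it is why the grouped comparison should be kept rather than deleted. It does not rescue the present wording, because the advantage requires a cut in the right place and the plan names none. A residual plot based on some 20 events would also have little ability to reveal non-linearity, so log-linearity is a real assumption.

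Second, scoring group may mean an assay's own categories, for instance for PD-L1 IHC. That is possible, and a reader should not infer that the plan commits to dichotomising every continuous marker or to searching for a cut: it says neither. But the documents define no such categories for cytokines, Kyn/Trp, TCR diversity, neoantigen burden or CyTOF fractions.

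Third, Kendall's tau already uses the full scale. It does, for PD-1, PD-L1 and PD-L2 only, and with no stated treatment of censored times.

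Fourth, the correlatives are exploratory, with no alpha or power assigned. That is correct. Power at a single two-sided 5% test is a yardstick for comparing methods, not a promise the plan has broken.

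Two further inferences fail. Nanostring transcripts should not be counted among the affected markers, since 13.1.2 gives that panel descriptive statistics. And section 2.5 does not present the trial as well powered for biomarkers. It says "This high rate of response will improve our statistical power in discovering novel biomarkers", which is a comparative statement about response rate, not about DOR, PFS or EFS.

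**Conclusion.** The point holds as a minor one. The only time-to-event biomarker test named rests on an undefined grouping, and for quantitative markers a full-scale Cox model is usually the stronger analysis of the same data.

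The loss is about 12 to 21 points of power for PFS, given 30 patients, about 20 to 23 events, a median split, a log-linear effect, HR per SD of 1.5 to 2.0 and two-sided 5%; EFS would be similar at the same event counts. It falls to about 7 to 12 points with a three-group trend test at about 20 events. For DOR it is about 3 to 17 points at the same HRs, with 18 responders and 9 to 12 events.

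A reader might take 12 to 21 points as a property of this trial, or apply it to DOR. The documents support neither: they give no effect size, event count, alpha or number of groups for these tests, and DOR uses a smaller set of patients. Under a true threshold at the cut the sign reverses. The effect is confined to exploratory analyses; the ORR decision rules and the primary conclusion are untouched.

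**What to change.** Replace the time-to-event sentence in 13.1.2 with wording to this effect:

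*The association of each quantitative biomarker with PFS, EFS and DOR will be tested in a Cox model with the biomarker on its continuous scale (log-transformed if skewed), reporting the hazard ratio per SD with its 95% CI. Ordered IHC scores will be tested with a one-degree-of-freedom trend test. Kaplan-Meier curves with log-rank tests by group will be a secondary display, using cut-points fixed before outcome data are examined.*

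For each marker displayed in groups, add the number of groups and the source of the cut (assay category, published value, or a quantile chosen in advance).

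The cost is a few lines of analysis text, with no new patients, samples or assays. The downsides are a log-linearity assumption that few events can check only weakly, some loss of power if the true effect is a threshold, and a hazard ratio per SD that is less direct to read than two curves. Keeping the grouped display covers part of the last two.
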